1 R34 DA0029871

**NCT01170026**

**7-1-13**

## **Study Design**

The project will begin with an open trial with 20 families to review and adapt the protocol. Then a two group randomized design will be used to test the primary hypothesis that an Individual Motivational Intervention (IMI) plus Family Check-Up (FCU) will lead to lower rates of SU and improved family management practices at follow-up among 13-16 year old adolescents in the truancy court program who report they have already begun to use substances compared to a group that receives psychoeducation (PE) plus Standard Care services provided by truancy court. Adolescents will be randomly assigned to the experimental condition (IMI/FCU) or the comparison condition (PE). All participants will complete baseline, 3 and 6 month follow-up assessments.

## **5B. Participants**

A total of 120 families (20 in open trial, 100 in RCT) with children primarily in mid-adolescence (commonly considered ages 14-16 years old) but some in early (13 years old) adolescence (Steinberg, 1999) will be recruited and randomized to receive either IMI/FCU or SC. **Inclusion criteria** are: (1) the target child is between the ages of 13-16 at the start of the project and living at home with at least one parent/guardian, (2) the target child must be seen in Truancy Court and must screen in with a t- score of 70 or above on one of the DSM-oriented scales (internalizing or externalizing problems) on the Child Behavior Checklist (i.e. reach the clinical cut-off), (3) the child must report 6 or more incidences of substance use in the last 90 days, and (4) parental consent and child assent are obtained. **Exclusion criteria** are: (1) adolescent meets diagnostic criteria for substance dependence suggesting need for more intensive services, and (2) the family is not able to speak and understand English or Spanish well enough to complete study procedures.

**Ethnic and gender considerations.** We expect to have approximately 60% to 70% boys in this sample. We will over-sample girls to lower the ratio of boys to girls. The ethnic racial distribution of Truancy Court is approximately 60% minority families, most of these being of Hispanic and low income status.

**Sample size projections.** Recruitment will take place in months 4 - 28. The RI Truancy Court has a current active roster of over 2,000 adolescents. In our pilot, we have worked with only one of the 4 magistrates in only 3 schools. If we consent approximately one-half of the referrals (in our pilot we have consented slightly more than half of referrals to date), baseline evaluations will easily be completed with about 100 families. This projection allows a 20% drop-out rate by 6 month follow-up ( $100 \times .8 = 80$ ).

**Piloting.** The PI, Co-I and treatment provider hired to conduct this study will each pilot 5-8 additional families at the start of this study. Final changes in the IMI/FCU will be made after these additional 20 families are piloted. Particular emphasis will be placed on adapting the school performance/attendance and sexual risk taking sections of both the individual and family motivational interventions.

**5B1. Procedure.** Parent(s) or legal guardian(s) (hereafter referred to as "parents") of adolescents in the targeted age range will be recruited from the RI Truancy Court Program (see letters of support). Following arraignment procedures, families will be given information about the project by study staff who will be present at all truancy court arraignments and who will also answer any questions parents may have. Interested participants will be contacted by study staff at their second Truancy Court arraignment appointment. During this meeting, they will receive an oral and written description of the study, including a description of the project procedures, number of appointments and compensation for participation, potential risks and benefits, and confidentiality. Families who provide parental consent and adolescent assent will be administered the screening battery. If the child does not meet the substance use and CBCL inclusion criteria, they will be given a package of educational materials regarding truancy and SU.

**Assignment of participants to conditions.** In the open trial portion, the first 20 families will receive the IMI/FCU in order to inform adaptations to the current protocol and to examine its feasibility and acceptance. After this open trial, 100 families will be recruited and randomized into either the experimental or the comparison control condition. These assignments will be made soon after completing the baseline assessment and through random assignment using the urn method (Stout et al., 1994). Urn randomization assigns participants in a given subgroup to intervention conditions, but systematically biases the randomization in favor of balance among the intervention conditions. Participants will be randomized according to gender, substance abuse (yes or no), and meeting CBCL cut-off for internalizing only versus externalizing only or externalizing/internalizing.

**5B2. Baseline and follow-up assessments (IMI/FCU and PE).** Parents and teens will complete the

assessment battery described below at their local school. In person follow-up assessments will be held at 3 and 6 months following the baseline assessment. An RA who will be blind to condition assignment will conduct each follow-up assessment. The follow-up assessment battery will be identical to baseline.

**5B3. Protection against attrition.** At baseline, multiple sources of contact information will be recorded for all adolescents and parent/guardians for the purpose of collecting follow-up data. We will obtain a release of information from parents in order to ask the school and truancy court for contact information during the time

period of the study. When applicable, the parent's cell phone number, employer phone number, and shifts at work will be recorded. Locator information will include name, address, phone number, relation to the patient, and the best times of day to reach the locator (**See Appendix 2**). Contact information will be updated by periodic phone calls and at each assessment session, including the names and telephone numbers of two friends or family members who can be contacted if research staff is unable to reach the family. Parents will be asked to sign a form letter addressed to each of the locators, which explains that they are participating in a research project with Brown University and that they have named this person as a locator. Locators will be contacted only if all efforts to reach the family fail. Participants will also be given refrigerator magnets and pens with contact information as well as a card with the dates for each of the subsequent follow-up assessments. Reminder postcards will also be sent out and phone calls will be made. Weekly case review meetings will be held between staff and the PI to review no-shows, non-verified and non-confirmed cases, and plans to complete contact with the participant. We have used these procedures with success in our current projects.

**Table 1. Timeline for assessment and intervention activities**

Design	Week 0	Week 1	Week 13	Week 25
	Baseline incl. video assess.	In person mtg.	3-month FU + Booster	6-month FU
IMI/FCU	X	feedback	X	X
PE	X a	education	X	X

Note. IMI/FCU = Individual MI/Family Check-Up ; PE = Psychoeducation.

aTwo video tasks only.

**Compensation for participation.** Parents and teenagers will each be compensated \$75 for the time it takes to complete baseline and \$75 for follow-ups.

### **5C1. Individual Motivational Interview/Family Check-Up Condition**

The experimental condition consists of both the individual motivational interview (IMI) for the adolescent and the Family Check-Up (FCU). Both adolescents and parents complete baseline assessment measures including videotaped interactional tasks in their first session.

Individual Motivational Intervention (Appendix 3). The basic MI described here has been used with over 200 adolescents in our previous studies. Because we are covering more material, i.e. alcohol, school behavior and performance and sexual risk-taking, we are adapting the original MI to take place over two sessions. It incorporates open-ended exploration, personalized feedback, and discussion about the adolescent's substance use, and the consequences of these behaviors. Our procedures incorporate the central principles described by Miller and Rollnick (1991). The intervention will consist of four components: establishing rapport, assessing motivation for change, motivational enhancement, and establishing goals for change. The first component, establishing rapport, aims to present the counselor as empathic, concerned, nonauthoritarian, and nonjudgmental. The session will begin by introducing the interview as a chance for the adolescent to talk about his/her thoughts and feelings about SU. The counselor will emphasize that the intention is not to tell the adolescent what to do, rather it is up to the adolescent to make decisions and choices about SU and things he/she does while using substances. Next, level of motivation for change will be assessed by asking the adolescents to talk about their likes and dislikes about SU. Open-ended questions and reflective listening statements will be used to encourage adolescents to generate as many salient positive and negative aspects of SU as possible, and to talk about the effects that matter most to them. The counselor then tailors the MI to these pros and cons. **In this application, the MI will be adjusted to address both truancy and sexual risk taking in addition to SU.**

Enhancement of motivation to change will be accomplished by utilizing the MI strategies of individualized normative feedback, examining decisional balance, and providing information and advice. The individualized feedback will be derived from the assessment and will be provided in both written and graphic formats to assist the adolescent in understanding the information. The feedback form will have the following six sections: 1) participant SU and normative information from age matched peers, 2) physical dependence on alcohol, marijuana, and other substances, 3) family risk, 4) consequences of SU use (i.e. truancy, engaging in unsafe sex practices), 5) attitudes toward peer substance use; and, 6) participant risk for STD/HIV and pregnancy and normative information for high school students. In the SU section information about marijuana use will be presented first followed by other drugs. The information will include frequency of marijuana use, drinking, and use of other substances, average number of joints, drinks and other incidences of drug use per week, frequency of heavy marijuana and other drug use and drinking, and average and peak BAC. In addition to providing concrete feedback, this section is designed to correct overestimations (i.e., the false consensus effect) common among adolescents about the prevalence of smoking marijuana, drinking and heavy drinking, and use of other substances (Baer et al., 1991) and to provide the opportunity to discuss the increased problems that are associated with episodic heavy substance use (Midanik & Clark, 1995). National data for substance use (i.e., marijuana, alcohol and other substances) among adolescents (Johnston et al., 2009; SAMHSA, 2007) will be used as a source for normative comparisons on frequency, quantity, and frequency of substance use. Information about BAC and metabolism also will be presented. The section on physical dependence will also address the fact that many adolescents are proud of their ability to tolerate marijuana and

alcohol and have misconceptions about tolerance. Adolescents who receive a family-history positive score will be informed that due to their parental substance abuse history, they are at greater risk for developing an SU disorder themselves. Substance-related consequences will be presented and comparisons will be made with norms for this measure. National data will also be presented and discussed for sexual risk taking behaviors (CDC, 2007). This feedback will include a section discussing the likelihood of engaging in unprotected sex while high or drunk and rates of STD/HIV and pregnancy among high school students. The feedback section is designed to increase the adolescents' motivation to alter risky behavior by helping them to recognize their susceptibility to harm and the costs of their behavior. For each of the feedback topic areas the counselor will review the feedback with the adolescent, elicit the adolescent's reaction, and provide further information when relevant. Counselors will explore which aspect of the feedback has raised the most concern and respectfully express their own concerns when necessary.

Following the presentation of the feedback, counselors will examine the patients' decisional balance by asking the adolescent to "envision the future," and to think about what positive things might happen if their SU were to decrease and what would be the worst thing that could happen if their SU were to stay the same. This part of the MI is designed to develop the adolescents' sense of discrepancy between current behavior and future goals, and should serve to increase the adolescents' ambivalence.

In the final phase of the intervention, the adolescent and counselor will collaborate to develop a plan for the future. This will include identifying goals for behavior change, exploring barriers to these changes, and providing strategic advice. A "goals sheet," which contains a variety of SU moderation goals, and harm reduction goals as well as some blank spaces for filling in other goals, including school attendance and performance, will be used here. Adolescents will be asked to select the preprinted goals that they would like to attempt and to generate other goals. This phase of the intervention was designed based on several research findings: first, that motivation is enhanced by encouraging participation in all decision-making regarding SU (Cooney et al., 1995), that using individualized strategies leads to more positive outcomes (Miller & Hester, 1986), and that most people prefer to select their own goals rather than having goals set for them (Sobell et al., 1993). Finally, it provides the opportunity for the counselor to support the adolescents' self-efficacy about making changes. At the completion of the session the counselor will provide the personalized feedback, the goals sheet, and informational handouts about SU to participants. In this adaptation, we expect the MI session takes about 90 minutes, spent over 2 sessions. The IMI covers the three constructs - intentions to use, normative beliefs about peer use, and attitudes towards peer use which have been shown to have the most consistent overall effects on adolescent SU (Stephens et al., 2009) as well as motivation to abstain which as been shown to have specific effects on marijuana use (King et al, 2009).

Family Check-Up (FCU). The FCU begins with using self-report assessments and the family videotape (FAsTask). The Research Assistant administers the self-report measures. The Treatment Providers administer the FAsTask in order to keep the RA who conducts the follow-ups blind to treatment condition as well as to observe the family interactions firsthand through a one-way mirror to assist in the feedback session.

Videotaped Family Assessment Task (FAsTask). The video-taped family problem-solving task format (Forgatch, 1989; Robin & Foster, 1989) adapted by Dishion et al. (1996a) will be used to assess parent-child interactions and provide additional assessment information for feedback in the FCU. A complete script of the FAsTask which will be adapted in order to make it more appropriate for truancy court families is included in Appendix 4. The following FAsTask was used in our previous projects with alcohol-positive teens. The proposed adaptations are included in **bold text**.

3 minutes	Parents and target child plan an activity (relationship quality)
5 minutes	Parents lead a discussion about a behavior they would like to increase and how they would encourage the process (encouraging growth).
5 minutes	Child leads a discussion about a time without supervision and parents seek additional information (monitoring)
5 minutes	Parents lead a discussion on setting limits over the previous month (limit setting)
5 minutes	Family discusses a "hot" family problem pre-selected by parents (i.e. problem solving)
5 minutes	Family discusses school performance and attendance issues and try to come up with a solution (problem solving-truancy)
5 minutes	Parents lead a discussion on the family beliefs about marijuana, alcohol, cigarettes and other SU (substance-use norms)
5 minutes	Teen discusses his/her observations on SU by teens and school attendance (peer relations)
5 minutes	Parents lead a discussion on their beliefs on how SU can result in risk taking behavior such as unprotected sex (risk behavior norms)

3 minutes Parents recognize a positive attribute of the target child (positive recognition)

These proposed adaptations may be modified or further adaptations may be considered based on feedback that is received during the open pilot trial.

FAsTask Clinical Coding. [name] was trained in the coding system for this task by [name] from the Oregon Research Institute and has created a structured clinical codebook that defines each item to be coded and gives specific examples of high and low-scoring observations ([see Appendix 4](#)). An inter-rater reliability estimate (i.e., % of ratings within two points on a 9-point scale) was created for ratings in our current trial. Percentage of inter-rater reliability within each case ranged from 71 to 96%, mean=86%. New codes will be created in the open trial for the new tasks developed for this adaption of the FAsTask.

All FAsTask videos will be coded by the Treatment Provider and the PI or Co-I, who will watch each segment of the videotape together and complete separate coding sheets. Ratings assigned to the family will then be discussed and consensus will be reached. When consensus cannot be achieved, the PI will review the tape segment to determine the coding. Ratings reached by consensus will be used during the feedback session. "Macro" clinical scores are calculated and coded as an area of "strength," "needs improvement," or "challenge," and provided as feedback during the Family Check-up session. Macro scores include positive relationships, monitoring, limit setting, problem solving, school importance and substance use norms. Norms were derived from 120 multi-ethnic families whose children had good school attendance and no disruptive problems in school (Dishion & Kavanagh, 2003). This coding method was used in Project REFRAME with 79 families and has been found to be the most effective method for coding the task for the purposes of providing feedback to families. These data along with parent self-report measures (see [Table 2](#)) will be used to generate the individualized feedback report for use in the parent feedback session.

Parent Feedback Session (FCU). The primary component of the FCU is feedback about the assessment (self-report and video) obtained at baseline. The measures provide data which are incorporated into the feedback given to the parents along with the FAsTask data ([see Appendix 5](#)) for how measures are tied into the FCU feedback for parents). A week after the family completes the baseline assessment including FAsTask, parents will participate in their feedback session (i.e., the FCU). In our current study, for families referred from the Emergency Department (ED), 20% never returned for the first family assessment session to complete the FAsTask. (**Note:** We do not anticipate this to be a substantial problem in this application because there is frequent contact between families and the Truancy Court compared to one time contact with the ED.) Nonetheless, of the 79 families randomized to the FCU who completed the FAsTask, 77 returned for the feedback sessions of the FCU. All of these sessions will be audiotaped to evaluate fidelity. The session, which is based on MI techniques (Miller & Rollnick, 2002), is designed to support appropriate parenting and provide motivation to change maladaptive parenting (Dishion & Kavanagh, 2003). The FCU supports the parents in limit setting and also addresses the parent/adolescent relationship, parental understanding of the autonomy needs of the adolescent and greater involvement in the peer activities of the adolescent (Dishion et al., 1996a). The principles and techniques utilized in the parent session are based on techniques with demonstrated effectiveness in engaging families and motivating them to change. These include approaching the change process collaboratively (Patterson & Chamberlain, 1994), sharing assessment results with parents to build collaboration (Sanders & Lawton, 1993), providing a flexible menu of resources in the community (Dishion & Owen, 2002) and supporting motivation to change.

Dishion and Kavanagh (2003) outline four specific phases of the feedback session: (1) Self-assessment: Parents are asked if they learned anything about their family from participating in the assessment. (2) Support and clarification: The interviewer supports the family's self-assessment efforts, assesses their level of understanding of the family, and clarifies issues within the family. (3) Feedback: In this phase, a summary form of the assessment findings is reviewed with the parents. Rather than give specific results from individual scales, this information is summarized into categories including family context (e.g., parent SU, life stress), parenting practice (e.g., monitoring and SU, school and sexual behavior expectations for teens), child behavior (e.g., positive behaviors, problem behaviors), and peer and sibling relationships (e.g., peer involvement with school, experimentation with drugs and alcohol). Normative information regarding escalation in SU rates from 7th through 12th grades is also presented. The August 26, 2009 release of the National Survey of American Attitudes on Substance Abuse XIV: Teens and Parents is cited which indicated that adolescents who have seen their parents intoxicated are more than twice as likely to get drunk themselves and three times as likely to use marijuana and smoke cigarettes. (4) Menu of options: Parent motivation for change and steps for making positive changes are discussed, including potential barriers to change. Parents are also asked to consider how they anticipate their child reacting to any proposed changes, problem-solving any potential negative reactions.

Booster Mailings (IMI/FCU only). Parents will receive brochures at 1-month intervals for 5 months. These brochures were used in REFRAME and are currently being used in the current trial and focus on SU and parenting ([see sample in Appendix 6](#)). These brochures help refresh the FCU content for parents in our trial.

3-Month Booster Sessions. Parents and adolescents will receive a booster session at 3-month follow-up. These booster sessions will review the content that was discussed during the IMI and FCU sessions. Interventionists will specifically focus on checking-in with participants regarding the action plans that were generated during their first session and ask about whether they were able to implement their action plans, what

the experience was like, and whether they experienced any other positive changes as a result. If the change plan was successfully implemented, participants will be encouraged to identify another change or goal that they would like to work towards and develop another action plan. If parents and adolescents either struggled or did not successfully implement their change plan, obstacles will be discussed along with strategies for overcoming these obstacles. Motivation, readiness, and confidence to change will also be discussed.

Interventionist Training (IMI/FCU). Manualized training in adolescent IMI for ongoing NIH-funded clinical trials has been conducted for over 10 years at our Center. The training sequence is approximately 30 hours in length and includes didactic presentations, viewing of the videotaped training series created by Miller and Rollnick (1998), readings on MI by Miller and Rollnick (2002), and extensive supervised role-plays...

Therapist training materials developed for our current FCU grant will be used for FCU training procedures (see Appendix 7). The training program includes the following components: 1) participation in the structured workshop on MI described above, 2) review of the FCU manual, 3) use of videotapes demonstrating examples of the FCU, and 4) functioning as a co-therapist using the FCU approach.

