### **5D. Measures (see Appendix 9 for non-copyrighted measures)**

**Rationale.** The measures for the assessment battery were chosen for three main reasons: first, to provide information and normative data whenever possible that can be used in the feedback portion of the FCU; second, to assess changes in outcomes over time; and third, to assess potential mediators. Although there are a large number of measures, most are brief. With the exception of the measures used specifically for feedback in the FCU (see bottom of Table 2), all measures will be administered to both groups. We felt it was important to conduct some form of dynamic (i.e., *in vivo*) assessment with both groups because changes in parenting behaviors and parent-child relationships are complex and may not be captured by self-report measures alone.

**Screening Measure.** Because teens seen at truancy court are very heterogeneous in their presentation, we will require that all participants meet minimum criteria for internalizing or externalizing disorders on the well-validated Child Behavior Checklist (CBCL). The CBCL (ASEBA: Achenbach & Rescorla, 2001) is a widely-used, parent-rated checklist to assess behavior problems. Well-accepted clinical cut-off scores on the internalizing or externalizing problems of the DSM-oriented scales ( $\geq 70$ ), that are reasonable indicators of youth with diagnosable psychiatric disorders, will be used to screen in for this study. The Timeline Follow Back (described below) will be used to assess the inclusion criterion of 6 or more instances of substance use in the prior 90 days. Teens will also be administered the Schedule for Affective Disorders and Schizophrenia for School- Age Children - Present and Lifetime Version (K-SADS- PL) Substance Use module to rule out substance dependence. The K-SADS-PL (Kaufman et al., 1997) is semi-structured diagnostic interview which

provides an assessment of DSM-IV psychopathology in children and adolescents. Inter-rater agreement on screens and diagnoses is high (range: 93% to 100%). The K-SADS is available at <http://www.wpic.pitt.edu/ksads/default.htm>.

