## 1. Background Variables

**Demographics.** Routine socio-demographic variables will be recorded including age, gender, race, school status, and history of mental health or substance use treatment. Locator information is also collected.

Table 2. Measures	Parent/Adol	Baseline	3 mos.	6 mos.
1. Background Demographics Locator Information	A/P A/P	X X	X	
2. Substance Use Parent Substance Use Adolescent Drinking Questionnaire (ADQ) Drug Use Questionnaire Timeline Follow-Back – Substance Use	P A A A	X X X X	X X X X	X X
3. Family Management Parent Monitoring Questionnaire (PMQ) Parent Reactions to Youth AOD Use Parent-Adolescent General Communication Scale Parent-Adolescent Alcohol and Drug Communication Scale Parent-Adolescent Sexual Communication Scale Conflict Behavior Questionnaire (CBQ) Video Code – Parent Limit Setting and Monitoring	A/P P A/P A/P A/P A/P A/P	X X X X X X X	X X X X X X X	X X X X
4. Other Problem Behaviors Child Behavior Checklist (CBCL) Reckless Behavior Questionnaire (RBQ) School Attendance - TLFB School Truancy and Performance Sexual History/Perceived Risk of HIV/STDs	P A A A A	X X X X X	X X X X X	X X X X X
5. Peer Influences Peer Use/Tolerance of Use Parental Management of Peers (PMPI) Peer Social Skills (Child) Peer Social Skills (Parent)	A A A P	X X X X	X X X X	X X X X
6. Teen Cognitions Marijuana Effect Expectancy Questionnaire Motivation to Abstain and Perceived Difficulty - Marijuana Youth Alcohol and Drug Survey Subscales Brief Situational Confidence Questionnaire	A A A A	X X X X	X X X X	X X X X
7. Substance Use and Mental Health Treatment History(CASA)	P	X	X	X
8. Intervention Acceptability Exit Interviews Session Evaluation Form	P P	X a X a		
9. Family Check-Up Only Measures Parent Substance-Related Beliefs Family Stress (on PSSC) House Rules Questionnaire Parent Support-Questionnaire FAsTask Video (10 tasks)	P P P P P/A	X X X X X		

aAdministered after 2-session intervention

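### The follow-up RA's blind is protected for the FCU video but not for four FCU-only parent questionnaires, and the passages on baseline content and timing conflict

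*Combined protocol and SAP*

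**What the plan says.** Section 5B2 states the commitment: "An RA who will be blind to condition assignment will conduct each follow-up assessment". The Family Check-Up paragraph of 5C1 then divides the FCU assessment into two parts. On the first part it says "The Research Assistant administers the self-report measures". On the second it says "The Treatment Providers administer the FAsTask in order to keep the RA who conducts the follow-ups blind to treatment condition".

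The Rationale in 5D qualifies its rule on who receives what with the words "With the exception of the measures used specifically for feedback in the FCU", and gives every other measure to both groups. Section 9 of Table 2 lists the excepted items. The parent forms begin "Parent Substance-Related Beliefs Family Stress (on PSSC) House Rules Questionnaire" and end with the Parent Support Questionnaire; the 10-task FAsTask video completes the block. All five items are marked at baseline and at no later visit.

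Other passages bear on timing and content:

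- 5B1 places random assignment soon after the baseline assessment is complete.
- 5C2 has PE families complete the same baseline assessment as IMI/FCU families.
- A footnote to Table 1 gives PE only two video tasks at Week 0, while the FAsTask Video Code paragraph in 5D describes a limited set of three.
- Table 1 heads its Week 13 column "3-month FU + Booster" and marks it for both arms.

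**The concern.** The sponsor's own reasoning in 5C1 is that contact with FCU-specific assessment could unblind the person who later interviews the family. That reasoning applies equally to questionnaires that only one arm receives. An RA who hands a parent the House Rules form would know the family is in IMI/FCU; an RA who runs a baseline without it could infer PE. Absence of the forms is as informative as their presence, so in principle all 100 randomized families are affected.

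The main exposure is Aim 2. Substance use is measured with the Timeline Follow-Back, a calendar interview that uses cues to aid recall, so the interviewer can influence the count. The plan deliberately does not use parents or peers as corroborators of teen use, and the breath alcohol test only defers an interview. RA blinding is the only masking the plan describes. Because 5e and 5f treat effect-size estimates as the trial's main quantitative product, any assessor bias would carry into the sample size of the next trial.

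**Working it through.** No formula applies and the plan states no figure to reproduce. The check sets the passages side by side.

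**Step 1: which measures does the RA give?** The sentence in 5C1 that assigns the self-report measures to the RA follows directly on one saying that the FCU starts from self-report assessments and the videotape. The FAsTask coding paragraph adds that parent self-report measures from Table 2 feed the FCU report. The natural reading therefore includes the FCU-only questionnaires. No passage assigns them to anyone else.

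**Step 2: how much does the safeguard cover?** Section 9 of Table 2 has five items: four parent questionnaires and one video. Only the video is moved to Treatment Providers, so the safeguard covers 1 of 5 items and leaves 5 − 1 = 4 with the RA.

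**Step 3: is the baseline RA also the follow-up RA?** This is not stated. But moving the video away from the RA protects the follow-up RA's blind only if that RA would otherwise be present at this stage. The stated purpose, "in order to keep the RA who conducts the follow-ups blind to treatment condition", makes a shared RA the likely reading.

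**Step 4: does the leak survive the conflict on timing and content?**

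| Reading | Supported by | Contradicted by | Does the RA learn the arm? |
|---|---|---|---|
| FCU-only forms given at baseline to IMI/FCU families | Table 2, 5D | 5B1 (no arm exists yet), 5C2 | Yes, if one RA does both |
| FCU-only forms given after assignment | 5B1, and 5D on content | Baseline marking in Table 2 | Yes, if 5C1 is followed and one RA does both |
| All families receive all forms before assignment | 5B1, 5C2 | 5D, Table 2 section 9; for video, Table 1 footnote | No |
| A different RA conducts follow-ups | Not excluded by 5B2 | Hard to square with the reason given in 5C1 | No |

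Every reading conflicts with some passage or sits badly with it. The two readings that respect the FCU-only restriction both lead to unblinding if a single RA is used.

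**Step 5: which outcomes are exposed?** Substance use rests on teen report collected at the RA-run visit. The Adolescent Drinking Questionnaire and the Drug Use Questionnaire supplement the calendar interview, but they are also teen reports. Truancy is different: it has its own calendar interview, but 5D section 4 also takes truancy and grade point average from school records, which do not depend on the RA.

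**The case against.** The strongest case on the other side is that the documents show loose drafting rather than a broken blind. Section 5C1 does not name the four forms, and its reference to self-report measures could mean only the common battery. No passage says the baseline and follow-up RA are one person. If 5B1 and 5C2 govern, either no arm exists when the forms are given or every family receives them, and nothing is revealed.

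Much of this stands. The shared RA is an inference, and the timing conflict is real. It does not remove the point: 5D and Table 2 expressly say the forms go to one arm, and under 5C1 as written no one but the RA is assigned to give them.

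Three stronger readings are tempting and are not supported:

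- *That the blind is certainly false at both follow-ups.* This needs both the shared RA and the FCU-only reading of baseline, and neither is settled by the text.
- *That the 3-month booster is a proven second leak.* Table 1 marks that column for both arms, interventionists run the boosters, and nothing says the RA sees who attends or that the booster precedes the interview. The content described in 5C1 does refer only to the IMI and FCU sessions, so a precaution is reasonable. Nor does the statement that the follow-up battery is identical to baseline show that the FCU-only forms recur; Table 2 marks them at baseline only.
- *That the bias can be expressed as a share of the anticipated effect.* The documents give no figure for interviewer bias and no basis for choosing one.

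**Conclusion.** The concern holds in conditional form. If the RA who administers the FCU self-report measures also conducts the follow-ups, and the four questionnaires go only to IMI/FCU families as 5D and Table 2 say, that RA can identify the arm, contrary to 5B2. The first condition is implied by 5C1 but not stated; the second is stated but conflicts with 5C2 and, on timing, with 5B1. The consequence is a risk of assessor bias of unknown size, chiefly in the Timeline Follow-Back substance use outcome; truancy is partly protected by school records. This does not invalidate the design. It is a gap in a safeguard that the sponsor already thought necessary, and it should be closed.

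**What to change.** 1. In the Family Check-Up paragraph of 5C1 and in section 9 of Table 2, assign the four FCU-only questionnaires to the Treatment Provider, to be given after assignment together with the FCU-only video tasks. The RA then gives only measures common to both arms.
2. Amend Table 1, the opening of 5C1 and 5C2 to match that timing, and reconcile them with 5B1. This is more than a wording change, because Table 1 and 5C1 now place the video in the Week 0 session, and the parent feedback paragraph counts its interval from a baseline that includes it. State one number of video tasks common to both arms.
3. Say in 5B2 whether the baseline and follow-up RA are the same person, and that the follow-up RA neither gives nor sees the FCU-only forms.
4. As a precaution, have the RA complete the 3-month assessment before any booster session, with the counselor arranging the booster. Record the RA's guess of arm at 6 months so that the success of the blind can be reported.

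The cost is a little more counselor time and some scheduling. The Treatment Provider already meets these families for the video. No outcome measure, sample size or intervention content changes.
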